Draft 3.0	19-Sep-2016	Updated according to changes as detailed in protocol amendment 2, dated 30-Jun-2015. Changes include (but are not limited to): 
 1. Addition of a lower dose bimagrumab 70 mg i.v. every 4 weeks for dose-response modeling. 2. Change in randomization ratio from 1:1:1 to 2:1:2:2 (1 referring to the additional 70 mg treatment group). 3. Change from a weight-based to fixed-dose treatment regimen. 4. Decrease in treatment duration from 52 weeks to 24 weeks. 5. Increase in post-treatment follow-up epoch from 4 weeks to 24 weeks. 6. Change in study objectives with the primary analysis planned when all patients have completed the double-blind treatment epoch (Week 24 [EOT]). 7. Changes to various inclusion criteria, including but not limited to: 
 a. Lower limit of age decreased from 65 to 60 years. b. Lower limit of BMI decreased from 16 to 15 kg/m². c. Commitment to a 10-week rehabilitation program and 56-week treatment no longer applicable. 8. Changes to various exclusion criteria. 9. Modifications to prohibited concomitant medications. 10. Changes to planned frequency of various study assessments.
Draft 3.1	03-Nov-2016	Revised according to recently created RAP Module 7.1, dated 26-Oct-2016.
Draft 4.0	27-Jun-2017	Revised according to changes as detailed in protocol amendment 3, dated 07-Apr-2017 and comments received on updated RAP Module 7.1, dated 25-Nov-2016.
Draft 5.0	03-Nov-2017	Revised RAP Module 3, dated 27-Jun-2017 according to clarifications on the protocol deviation section and updates relating to the unblinding

Version	Date	Changes
		procedure. Also, revised based on comments received on updated Module 7.1, dated 27-Jun-2017.
Draft 6.0	18-Apr-2018	Revised RAP Module 3, dated 03-Nov-2017 according to changes detailed in protocol amendment 4, dated 19-Jan-2018 and comments received on dry run 1 outputs (TLFs) primarily on epoch displays, changes to subgroups etc.
Final 1.0	29-May-2018	Revised according to comments received on updated RAP Module 3 & Module 7.1, dated 27APR2018 and comments received on dry run 2 outputs (TLFs) primarily on in-text tables, formatting etc.
Amendment 1.0	22-Jun-2018	Revised according to comments received primarily on in-text tables, formatting etc.

██████████. BMI: Body mass index. EOT: End of treatment. SAF: Safety analysis set.

2.11.4	Adverse events related to study drug by primary system organ class and preferred term	54

eCRF	electronic Case Report Form
ECG	electrocardiogram
EDC	electronic data capture
EOS	end of study
EOT	end of treatment
██████	██
FAS	full analysis set
GFR	glomerular filtration rate
██████	████████████████████
HIV	human immunodeficiency virus
INR	international normalized ratio
i.v.	intravenous

IRT	Interactive Response Technology
LBM	lean body mass
LFT	liver function test
LLN	lower limit of normal
LSM	least squares mean
MAR	missing at random
MCP-Mod	multiple comparison procedure – modeling
MDRD	modification of diet in renal disease
MedDRA	Medical Dictionary for Regulatory Affairs
MMRM	mixed model repeated measures
MMSE	Mini Mental State Examination
NB	Negative Binomial
NMQ	Novartis MedDRA query
OC	Oracle clinical
█	████████████████████
█	██
█	██
█	██
█	████████████████████
PP	per protocol
█	██
█	██
PT	preferred term
RAP	report and analysis plan
REML	residual/restricted maximum likelihood
RDC	remote data capture
SAE	serious adverse event
SAF	safety analysis set
SBP	systolic blood pressure
SD	standard deviation
SMQ	standardized MedDRA query
SOC	system organ class

SPPB	short physical performance battery
TEAE	treatment-emergent adverse event
TESAE	treatment-emergent serious adverse event
ULN	upper limit of normal
UTE	unsatisfactory therapeutic effect
VAS	visual analog scale
VEGF	vascular endothelial growth factor

1 Statistical methods planned in the protocol and determination of sample size

[figure not shown]
[REDACTED] data will be analyzed by the [REDACTED] biostatistics team according to Section 9 (Data analysis) of the study protocol (protocol amendment 4), available in Appendix 16.1.1 of the clinical study report (CSR). Important information is provided in the following sections and details are provided, as applicable, in Appendix 16.1.9 of the CSR.

[figure not shown]
2 Statistical and analytical plans

2.1 Study objectives

Objective	Analysis Addressed in this Report and Analysis Plan (RAP)
2.1.1 Primary objective	
The primary objective is to assess the effect of bimagrumab given intravenously every 4 weeks on total lean body mass (LBM) assessed by dual energy X-ray absorptiometry (DXA) as assessed by change from Baseline at Week 24 relative to placebo in patients with disuse atrophy after surgical treatment of hip fracture.	Yes
2.1.2 Secondary objectives	
1. To assess the effect of bimagrumab compared to placebo on improvement in mobility as assessed by change from Baseline at Week 24 in derived gait speed (m/sec).	Yes
2. To assess the effect of bimagrumab compared to placebo on improvement in physical performance as assessed by change from Baseline at Week 24 in the Short Physical Performance Battery (SPPB).	Yes
3. To assess the post-treatment difference of bimagrumab compared to placebo on improvement in physical performance and mobility as assessed by change from Baseline at End of Study (EOS) in: 3.1 Derived gait speed (m/sec). 3.2 SPPB.	Yes

Objective	Analysis Addressed in this Report and Analysis Plan (RAP)
4. To assess the clinical safety and tolerability of bimagrumab relative to placebo as assessed by measures such as adverse events (AEs), clinical laboratory variables, electrocardiogram (ECG), vital signs, echocardiogram, X-ray assessment of the surgical procedure and potential orthopedic complications.	Yes
5. To evaluate the effect of bimagrumab compared to placebo on the incidence of falls.	Yes

Derived gait speed (m/sec): 4 meters (m) divided by the time in seconds (sec). [Peel et al \(2012\)](#)

2.2 Study design

This is a Phase IIa/IIb, parallel-group, randomized, double-blind, placebo-controlled, 24-week treatment, followed by a 24-week follow-up, multicenter clinical study (see [Figure 2.1](#) [Study design]). A screening epoch of up to 6 weeks post-surgery will be used to assess eligibility, followed by a treatment epoch of 24 weeks and a post-treatment follow-up epoch of 24 weeks. At the Baseline visit, eligible patients will be assigned to one of the following four treatment groups in a ratio of 2:1:2:2:

Treatment group 1: Placebo intravenous (i.v.) every 4 weeks.

Treatment group 2: Bimagrumab 70 mg (milligram) i.v. every 4 weeks.

[figure not shown]
Treatment group 3: Bimagrumab 210 mg i.v. every 4 weeks.

Treatment group 4: Bimagrumab 700 mg i.v. every 4 weeks.

Approximately 245 male and female patients aged 60 years or older, with successful surgery after low-energy hip fracture, will be randomized in more than 60 centers worldwide. Since the 70 mg dose is expected to be a non-effective or minimally effective dose it will be used only for dose-response modeling and not hypothesis testing, therefore fewer patients will be randomized to this group.

Randomized patients will be treated for 24 weeks and will receive study drug every 4 weeks for a total of 6 infusions. The first infusion will be given on Day 1 and the last infusion at the Week 20 visit with end of treatment (EOT) assessments performed 4 weeks later at Week 24 (or following premature discontinuation of treatment in the treatment epoch).

Figure 2.1 Study design

Patients who are screening failures for temporary reasons (i.e. inability to meet all of the inclusion criteria at the first screening attempt) can be re-screened once, unless they are outside of the 3 to 42-day post-surgery window. They should be re-consented and will receive a new patient number.

2.3 Treatment pooling and handling of pre-amendment 2 patients

Patients randomized prior to implementation of protocol amendment 2, dated 30-Jun-2015, were receiving a weight-based dose and were to be treated for 52 weeks. After consenting to protocol amendment 2, their treatment regimen was converted in a blinded manner via the Interactive Response Technology (IRT) system to a fixed-dose treatment regimen at their next scheduled visit. Patients on 3 mg/kg bimagrumab were converted in a blinded manner to 210 mg bimagrumab fixed dose and patients on 10 mg/kg bimagrumab were converted in a blinded manner to 700 mg bimagrumab.

Patients who had already completed Week 20 had their EOT (Week 24) assessments performed at their next scheduled visit after which they continued the study as per protocol amendment 2. Patients randomized prior to implementation of protocol amendment 2 may therefore have been treated for more than 24 weeks (more than 6 infusions).

Patients who entered the study prior to protocol amendment 2 will be pooled with fixed-dose patients as follows:

Table 2.1 Treatment pooling

Time of Entry into Study	Randomized	Analyzed
Prior to protocol amendment 2*	Placebo	Placebo
	Bimagrumab 3 mg/kg	Bimagrumab 210 mg
	Bimagrumab 10 mg/kg	Bimagrumab 700 mg

After protocol amendment 2	Placebo	Placebo
	Bimagrumab 70 mg	Bimagrumab 70 mg
	Bimagrumab 210 mg	Bimagrumab 210 mg
	Bimagrumab 700 mg	Bimagrumab 700 mg

*For patients who entered the study prior to protocol amendment 2 and potentially treated for more than 6 months (24 weeks).

Subsequently, for the pre-amendment 2 patients potentially treated for more than 24 weeks (more than 6 infusions), the treatment epoch, as used for analysis purposes, is defined as the first 24 weeks of treatment only i.e. start of the first infusion of study drug (Day 1) to last infusion of study drug cut-off at Week 20 + 4 weeks. Implying a total of 6 infusions within the defined 24-week treatment epoch.

Taking the aforementioned defined 24-week treatment epoch into account, the same conventions for defining treatment-emergent events (as well as assessments with clinically notable criteria defined, such as laboratory assessments, vital signs, electrocardiogram etc.) and for identifying concomitant medications will apply for all patients regardless of whether they were randomized pre- or post-amendment 2:

- Treatment-emergent: AEs will be deemed treatment-emergent if the date of onset or worsening of the AE is on or after the start of the first infusion of study drug (Day 1) until the last infusion of study drug (expected per protocol at Week 20) + 56 days.
- Concomitant definition: Concomitant medications defined as any medication which started or stopped on or after the start of the first infusion of study drug (Day 1) up to the last infusion of study drug (expected per protocol at Week 20) + 56 days or is ongoing.

In addition, analysis and presentation of patients' data beyond Week 24 (end of defined treatment epoch) will be handled as follows:

- Study drug administration data (Actual exposure to study drug [days] and exposure to study drug [days], cut-off): For pre-amendment 2 patients potentially treated for more than 24 weeks (more than 6 infusions), study drug administration data after Week 20 will be recorded in the Dose administration record – infusion electronic case report form (eCRF). For both pre- and post-amendment 2 patients, exposure to study drug will therefore be summarized by actual exposure days based on overall treatment duration, regardless of the defined 24-week treatment epoch (i.e. disregarding the cut-off at 6 months [24 weeks] treatment) and days exposed within the defined 24-week treatment epoch:
 - Actual exposure: ([Actual last infusion date + 56 days] – First infusion date) + 1 day.
 - Exposure, cut-off: ([Last infusion date, within the 24-week defined treatment epoch + 56 days] – First infusion date) + 1 day.
- DXA assessment data recorded after Week 24, for example at Week 36, Week 48 or Week 52, in the Body composition –DXA eCRF will be listed in by-patient data listings only. Subsequently, if treated for more than 6 months, the defined treatment epoch will comprise the first 24 weeks of treatment only as described above. The change in DXA assessments will be analyzed based on the first 24 weeks of treatment only as applied for all patients in the study, whether they were randomized pre- or post-amendment 2.

The same conventions and definitions will be applied whether the patient completes treatment or prematurely discontinues treatment or study. Similarly, regardless if the analysis is performed at the time of the primary or final update analysis.

[Appendix 3](#) (Data collection tool [eCRF] differences pre- and post-protocol amendment 2) details the differences in data collection pre- and post-protocol amendment 2. For variables that were only collected and recorded for patients enrolled pre-amendment 2 (N = 14) relevant data will be presented in by-patient data listings only and no further details with regards to these variables are included in the subsequent sections.

[Appendix 4](#) (Data collection tool [eCRF] differences pre- and post-protocol amendment 3) details the differences in data collection pre- and post-protocol amendment 3.

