In order to properly assess dose response relationship of bimagrumab at least three doses are required, ranging from a potential minimally effective dose to a dose where maximal efficacy is expected. A lower dose arm of 70 mg i.v., which is expected to show suboptimal to minimal efficacy, has therefore been added to this study. This will facilitate an adequate dose-selection for phase III without the need for supportive data from another dose- response finding study.

Changes to the protocol

[figure not shown]
Changes to specific sections of the protocol are shown in the track changes version of the protocol using ~~strike through red font for deletions~~ and red underlined for insertions.

[figure not shown]
The informed consent of the study will be amended. A copy of this amended protocol will be sent to the Institutional Review Board (IRBs)/Independent Ethics Committee (IECs) and Health Authorities.

The main changes are the following:

- Addition of a treatment arm and change dosing regimen from weight based dosing (bimagrumab 3 mg/kg and 10 mg/kg) to fixed dosing (bimagrumab 70 mg, 210 mg and 700 mg)
- Changing the randomization ratio from 1:1:1 to 2:1:2:2 (1 referring to the lowest dose group of 70 mg)
- Reduction of the treatment epoch from 52 weeks to 24 weeks and the respective number of infusions from 13 to 6
- Increase of the post treatment follow-up epoch from 4 weeks to 24 weeks
- Increase of the screening epoch to be from 7 to 28 days to 3 to 42 days post-surgery
- Modification of the secondary objectives to address the shorter treatment duration

- 
- Modification of the inclusion criteria
 - Lower limit of age has been decreased from 65 to 60 years
 - Lower limit of BMI has been decreased from 16 to 15 kg/m²

- 
- Modification of the exclusion criteria
 - History of fracture was clarified to recent lower limb fracture or surgery with persistent negative impact. By doing so 2 criteria were merged
 - Various criteria on condition affecting the patient's ability to walk (e.g. some visual, psychiatric or respiratory disorders) were merged bringing 5 criteria into one
 - Criteria on disease affecting food absorption was clarified
 - Exclusion of rheumatoid arthritis patients was removed
 - Vitamin D deficiency exclusion is limited to patients not receiving an appropriate loading dose
- 

- Abnormal liver function test criteria was clarified and liver disease are limited to present conditions

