9.2 Analysis sets

The Full Analysis Set (FAS) used for all efficacy analyses will consist of all randomized patients who received at least one dose of investigational treatment. Patients will be analyzed according to the treatment they were assigned to at randomization. Patients who entered the study before Amendment 2 will be pooled with fixed-dose patients as follow: bimagrumab 3 mg/kg patients will be analyzed as member of the 210 mg group, bimagrumab 10 mg/kg patients will be analyzed as member of the 700 mg dose group.

The safety (SAF) Analysis Set will consist of all patients who received at least one dose of study medication. Patients will be analyzed according to the treatment received. Patients who entered the study before Amendment 2 will be pooled with fixed-dose patients as detailed for the FAS.

Per-protocol (PP) Analysis Set will include all FAS patients who complete the study without major deviations from the protocol procedures. Major protocol deviations and the definition of the PP set will be identified and finalized based on blinded review of the data, prior to the data extraction for the primary analysis (EoT) and the global study team group level unblinding.

For patients who entered the study before Amendment 2 and have been treated for more than 6 months, data collected after the Week 24 visit will be listed.

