2.11.1 General adverse events

Adverse events will be categorized based on date of onset or worsening relative to the first and last infusion of study drug as:

- Pre-treatment: Date of onset or worsening of the AE is prior to the start of first infusion of study drug.
- Treatment-emergent: Date of onset or worsening of the AE is on or after the start of the first infusion of study drug until the last infusion of study drug (expected per protocol at Week 20) + 56 days (see [Section 2.3](#) [Treatment pooling and data handling of pre-amendment 2] for more details).
- Post-treatment: Date of onset or worsening of the AE is after the date of last infusion of study drug (expected per protocol at Week 20) + 56 days.

Missing or incomplete AE onset dates will be imputed prior to categorization; algorithms for date imputations will be provided in RAP Module 8 (Programming Specifications). No imputation will be applied to AE end dates. Hence, if the end date is missing, the duration of the AE will be “continuing”.

All AEs reported will be listed. With the exception of the overview presentations, primarily only TEAEs/Post-treatment AEs will be summarized for each treatment group and across active bimagrumab treatment groups combined (“Active Total: Safety” - Includes bimagrumab 700 mg, bimagrumab 210 mg and bimagrumab 70 mg), overall and by region (Japan/Non-Japan) (see [Section 2.6](#) [Subgroups]). Percentages (%) will be derived relative to the number of patients “at risk” (in SAF analysis set or ongoing at the start of follow-up). At the time of the primary analysis number of patients “at risk” comprises:

- Incidence of AEs at Screening: All enrolled patients implying all patients who provided informed consent.
- Incidence of AEs in treatment: Patients assigned to the SAF analysis set regardless of study status, implying all patients entering the 24-week treatment epoch.
- Incidence of AEs in post-treatment follow-up:
 - Patients who completed treatment but are ongoing in post-treatment follow-up or who have discontinued during post-treatment follow-up.
 - Patients who prematurely discontinue treatment within the defined 24-week treatment epoch and who then continue study participation as part of the planned 4-week post-treatment follow-up.
 - Patients who completed treatment and post-treatment follow-up (study completed at the time of the primary analysis).

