* For pre-amendment 2 patients, cut-off at Week 20 + 56 days. ** For patients who discontinued during treatment epoch, the target visit day values are EOT (derived) + 84 days and EOT (derived) + 168 days for Week 36 and Week 48, respectively. In addition, for the discontinued patients, the start day of the Week 48 visit name is 1 day after last infusion of study drug + 56 days (for pre-amendment 2 patients, cut-off at Week 20) + 126 days.

Realignment per assessment type (not following the general realignment of visits) is presented in Tables 3.2 to 3.7 below:

Table 3.2 Laboratory: Hormones /ECG

Study Epoch	Visit Name	Target Visit Day	Start Day of Visit Window	End Day of Visit Window
Screening	Screening	Day -39 to -1		
Treatment	Day 1	Day 1		
	Baseline	Defined as the last available assessment (scheduled or unscheduled) prior to the start of the first infusion of study drug, including pre-dose assessments at Day 1.		
	Week 12	Day 84	2	126

	Week 24	Day 168	127	Last infusion of study drug + 56 days *
	End of Treatment (derived)	End of Treatment is defined as the last available assessment (scheduled or unscheduled) assigned to treatment and including the 56-days *.		
Post-treatment Follow-up	Week 48	336**	1 day after last infusion of study drug + 56 days *	Last known date in study
	End of Study (derived)	End of Study is defined as the last available assessment (scheduled or unscheduled) assigned to the study.		

* For pre-amendment 2 patients, cut-off at Week 20 + 56 days. ** For patients who discontinued during treatment epoch, the target visit day values are EOT (derived) + 168 days at Week 48.

Table 3.3 Safety Laboratory: Hematology/Chemistry/Urinalysis

Study Epoch	Visit Name	Target Visit Day	Start Day of Visit Window	End Day of Visit Window
Screening	Screening	Day -39 to -1		
Treatment	Baseline	Defined as the last available assessment (scheduled or unscheduled) prior to the start of the first infusion of study drug, including pre-dose assessments at Day 1.		
	Week 4	Day 28	1	42
	Week 8	Day 56	43	70
	Week 12	Day 84	71	126
	Week 24	Day 168	127	Last infusion of study drug + 56 days *
	End of Treatment (derived)	End of Treatment is defined as the last available assessment (scheduled or unscheduled) assigned to treatment and including the 56-days *.		
Post-treatment follow-up	Week 48	336 **	Last infusion of study drug + 56 days * + 1 day	Last known date in study

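### In pre-Amendment 2 patients dosed past Week 24, on-drug gait-speed and SPPB tests from Day 197 enter the post-treatment Week 36/48 analyses, although the protocol says these data will be listed

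*SAP*

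**What the plan says.** SAP 2.3 explains that patients randomized before Amendment 2 "were to be treated for 52 weeks", and that they "may therefore have been treated for more than 24 weeks (more than 6 infusions"). For analysis, however, "the treatment epoch, as used for analysis purposes, is defined as the first 24 weeks of treatment only". The footnote to SAP Table 3.1 carries this into the visit windows: "For pre-amendment 2 patients, cut-off at Week 20 + 56 days". Later assessments belong to the post-treatment follow-up epoch, in the windows named Week 36 and Week 48.

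Protocol 9.2 has a different rule. For patients who entered before Amendment 2 and were "treated for more than 6 months, data collected after the Week 24 visit will be listed". SAP 2.3 gives a listing-only rule for DXA recorded after Week 24, and no such rule for SPPB or gait speed. SAP 2.14, which collects departures from the protocol, has a general entry on epoch presentation but does not mention the listing rule.

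For adverse events, SAP 2.11.1 has the category "Post-treatment: Date of onset or worsening of the AE is after the date of last infusion of study drug", with Week 20 in brackets as the expected time of that infusion and 56 days added. SAP 2.3 introduces the matching treatment-emergent definition as taking the 24-week epoch into account.

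**The concern.** One secondary objective (Protocol 2.2, SAP 2.1.2 item 3) asks how gait speed and SPPB compare with placebo after treatment has stopped. It is analysed by MMRM on the windowed visits up to Week 48 (SAP 2.10.2.3). A patient still receiving four-weekly infusions on Day 252 is not off drug, yet the windowing counts that visit as post-treatment Week 36.

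The direction of the error is foreseeable. Protocol 6.4.5 reports that in sporadic inclusion body myositis the functional benefit vanished when LBM returned to baseline after withdrawal. If hip fracture patients behave in the same way, on-drug values in an off-drug mean make the effect look more durable than it is. The protocol's listing rule would have kept these values out.

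The same cut-off may also govern which adverse events count as treatment-emergent. If it does, events that occurred on drug are counted as post-treatment.

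**Working it through.** **Inputs.** Visit days are from Protocol Table 6-1: Week 20 = Day 140, Week 24 = Day 168, Week 36 = Day 252, Week 48 = Day 336. The window rules are from SAP 3.5.1. The old schedule of 13 infusions comes from the Amendment 2 summary ("the respective number of infusions from 13 to 6") and is used only for past dosing dates. The 14 patients are from SAP 2.3, and the 245 randomized and 120 expected 48-week completers from Protocol section 4.

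**1. Reproduce the plan's windows.** The Week 48 window starts at the midpoint plus one day: (252 + 336)/2 + 1 = 295, as in Table 3.1. The Week 36 window ends at 252 + 42 = Day 294, which is consistent.

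**2. Apply the footnote.** 140 + 56 = Day 196, so the post-treatment Week 36 window opens on Day 197 whether or not dosing continued. Two of the assessment-specific window tables are not visible in the public copy. The SPPB schedule in Protocol Table 6-1 matches Table 3.1, so I take Table 3.1 to apply.

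**3. Lay the 13-infusion schedule over the windows.** Infusion visits on Days 168 and 196 stay in the treatment window. Days 224, 252 and 280 fall in follow-up Week 36, and Days 308 and 336 in follow-up Week 48. Up to 5 of 13 infusion visits are thus labelled post-treatment.

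**4. Compare with the actual last infusion + 56 days**, the SAP's rule for everyone else:

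| Last infusion (total infusions) | + 56 days | Days labelled post-treatment too early |
|---|---|---|
| Day 168 (7) | Day 224 | 224 − 196 = 28 |
| Day 196 (8) | Day 252 | 252 − 196 = 56 |
| Day 280 (11) | Day 336 | 336 − 196 = 140 |
| Day 336 (13) | Day 392 | 392 − 196 = 196 |

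A test on Day 252 is within 56 days of dosing only if the patient had at least 8 infusions; a test on Day 336 needs at least 11. A patient with 7 infusions is already 252 − 168 = 84 days off drug at Week 36.

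**5. Size.**
- Share of the trial: 14/245 = 5.7% at most. The number dosed past Week 24 is not stated (range 0 to 14).
- Ceiling per arm: under the earlier 1:1:1 allocation, 14/3 = 4.7 patients. A 2/7 arm of 120 completers has 120 × 2/7 = 34.3. The ratio is 4.7/34.3 = 13.6%.
- If drug gives 1.0 SPPB point while taken and nothing afterwards (assumed), the spurious effect is 0.136 × 1.0 = 0.14 point.
- Same ceiling with the trial's expected retention in the numerator: 120/245 = 49%; 4.7 × 0.49 = 2.3; 2.3/34.3 = 6.7%, or 0.07 point. This still assumes that every retained patient is on drug.

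**6. Adverse-event rates.** SAP 2.11.6 adjusts treatment-emergent AESI rates by actual exposure, which SAP 2.3 defines without the 24-week cut-off. SAP 2.9.1 defines total patient-years with the cut-off. If the event count is capped and actual exposure is not, numerator and denominator cover different periods and the rate is too low.

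**The case against.** Several points limit the concern, and most of them stand.

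- **Few patients, probably fewer than 14.** Patients beyond Week 20 when Amendment 2 took effect went to their end-of-treatment visit at the next scheduled visit (Protocol 5.2), and the others moved to the six-dose schedule. A reader might take 14% of an arm and 0.14 point as the expected bias. The documents do not support that, because it needs all 14 patients to be retained and still on drug at the late visits.
- **The safety half is not settled.** A reader might infer that on-drug adverse events are definitely removed from the treatment-emergent tables. The window tables need an explicit footnote to impose the cap, and the adverse-event definition carries none. Taken literally, the last infusion there is the actual one. The reference to the 24-week epoch in SAP 2.3 points the other way, so both readings remain open.
- **Events are not lost.** Adverse events are also summarized by study-day interval (SAP 2.11.1 and 2.11.3), and notable laboratory values over the entire study (SAP 2.11.7).
- **A partial check exists.** Pre- versus post-Amendment 2 is a planned subgroup (SAP 2.6), and SAP 2.10.2.2 summarizes gait speed and SPPB by it. The post-Amendment 2 stratum is free of these patients. But those summaries are descriptive and leave the pooled Week 36/48 MMRM as it is.
- **Boundary and wording.** Relabelling starts on Day 197, not at Week 24. The protocol says listed, not only listed, though listing in place of analysis is the natural reading.

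The SAP 2.14 entry on epoch presentation is not enough to answer the concern: it does not tell the reader that a protocol rule was set aside for SPPB and gait speed.

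**Conclusion.** The protocol and SAP conflict on how to handle post-Week 24 SPPB and gait speed in pre-Amendment 2 patients dosed past Week 24. Followed as written, the SAP puts on-drug or recently stopped values into an off-drug estimate and does not declare the departure. The bias is towards durability, provided that an on-drug benefit exists and fades after stopping. It is small: 0 to 14 patients, with 0.14 SPPB point as a ceiling under the assumptions above and 0.07 point once retention is applied.

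It would be wrong to infer that the main results are at risk. The primary LBM test and the gait-speed and SPPB tests in the fixed sequence are at Week 24, whose window closes on Day 196. They are not affected. For adverse events the conclusion is only that the cut-off is ambiguous and that event counts and exposure may not match.

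**What to change.** - Flag every patient with an infusion after the Week 20 visit. List their SPPB and gait speed after Week 24, and leave these values out of the Week 36/48 MMRM and summaries, as Protocol 9.2 states.
- State in SAP 2.3 and 2.11.1 that treatment-emergent adverse events and notable values run to the actual last infusion + 56 days.
- Use one cut-off for both events and exposure in the AESI rates.
- Record any remaining departure from Protocol 9.2 in SAP 2.14, and report how many patients carry the flag.

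The cost is SAP wording and one derived flag, since infusion dates after Week 20 are already collected (SAP 2.3). The downside is that up to 14 patients leave the Week 36/48 efficacy summaries, including some late values that are genuinely off drug.
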